## 2.2 Purpose and Trial Objectives

The aim of the study is to assess procedural completion, the post-operative stone clearance (Day 30) and the safety profile following robotic mini-Percutaneous Nephrolithotomy (PCNL) performed with the MONARCH™ Platform, Urology. Additional objectives include exploring immediate post-operative outcomes (Day 1), patient-reported outcomes, and outcomes related to retreatment, percutaneous access, and surgeon experience. Data gathered from this study will also be used to optimize the robotic platform.

## 3. Investigational Plan

### 3.1 Trial Endpoints

#### Primary Endpoint

The primary endpoint is the completion of the robotic-assisted mini-PCNL kidney stone removal procedure, defined as using robotic-assistance provided by the MONARCH™ Platform, Urology to achieve the following procedure milestones:

- Gain safe concomitant (i.e., retrograde and antegrade) access to the upper urinary tract
- Locate and visualize kidney stones
- Enable fragmentation of stones by standard of care method
- Evacuate stone fragments and dust
- Complete treatment without need for case conversion, as assessed by the investigator

#### Secondary Endpoints

The following will be considered secondary endpoints:

- Stone free rate ( $\leq 4$  mm residual fragments, measured 30-days post-operative)
- Adverse events through 90-days post-operative, scored on the Clavien-Dindo scale (see Appendix III)
- Conversion to conventional treatment methods due to study device-related safety event

#### Additional Data Collection, includes, but is not limited to:

##### *Demographics and Medical History:*

- Age (years) at time of procedure
- Sex, Race, Ethnicity, BMI
- Medical history (including prior history of stone disease and treatment)

##### *Pre-Operative:*

- Parameters of kidney stone number, size, density and location via CT
- PROs (baseline)

The electronic version of this document is stored in Agile PLM and is considered the controlled copy.

Printed copies are for reference only and considered UNCONTROLLED.

CONFIDENTIAL AND PROPRIETARY OF AURIS HEALTH, INC.

 AURIS	PROTOCOL	Doc #:	104-016667-00
	Monarch Uro - Post-Operative Outcomes Study (2023-URO-0001)	Rev:	C
		Page:	14 of 52

*Pre-Procedure:*

- Date and time patient admitted to hospital
- Cystoscopy phase timestamps and fluoroscopy use
- Patient positioning parameters

*Procedure:*

- Timestamps and additional parameters during procedure phases of device setup, ureteroscopy, percutaneous access, mini-PCNL setup, mini-PCNL procedure, and device teardown
- Intraoperative visualization
- Intraoperative fluidics management
- Intraoperative bleeding
- Conversion to conventional procedure (and reason for conversion)
- Presence of Randall's plaques
- Urologist experience survey

*Discharge and Follow-up:*

- Any placement of a ureteral stent or nephrostomy tube
- Date and time subject is discharged from hospital
- Any additional stone retreatment during follow-up
- Assessment of any residual stones via CT (post-operative Day 1 and Day 30 (as needed))
- PROs (post-operative Day 1, 30, and 90)

The following endpoints will be derived from the data collected:

- Percutaneous access success rate
- Percutaneous access time
- Procedure duration
- Hospital length of stay
- Radiation time and dosage
- Stone removal efficiency (stone burden/lasing time)
- Retreatment rate: post-operative Day 30 and Day 90
- Stone free rate: post-operative Day 1 and Day 30
  - Sub-analyses will include calculations using various thresholds for residual fragments (e.g., 0 mm,  $\leq 2$  mm, and  $\leq 4$ mm)

**3.2 Trial Design**

This study is designed as a prospective, single arm study of the robotic-assisted removal of kidney stones using the MONARCH™ Platform, Urology system. Subjects presenting with kidney stones determined to be appropriate for a mini-PCNL procedure per standard medical care and who meet study inclusion and exclusion criteria will be invited to participate. This study will enroll up to 60 subjects. The number of subjects enrolled per site may vary, with maximal enrollments per site determined considering factors such as patient variability, speed of enrollment, and availability of disposable instruments & accessory devices.

The electronic version of this document is stored in Agile PLM and is considered the controlled copy.

Printed copies are for reference only and considered UNCONTROLLED.

CONFIDENTIAL AND PROPRIETARY OF AURIS HEALTH, INC.

	PROTOCOL	Doc #:	104-016667-00
	Monarch Uro - Post-Operative Outcomes Study (2023-URO-0001)	Rev:	C
		Page:	15 of 52

**Inclusion of Left and Right Kidney Procedures within a Subject:** A subject may obtain the study procedure in both kidneys at the discretion of the Sponsor, provided: the case is pre-reviewed with the Sponsor, and the timing of the second study procedure is reasonably not expected to interfere with the interpretation of results from the previous procedure (e.g., causality of any adverse event). Analysis approach for study data is described in Section 8.5. Use of the study device to perform any procedure in a contralateral kidney without prior approval from the Sponsor is not permissible.

**The study device (MONARCH™ Platform, Urology and its Instruments and Accessories) will only be used to perform the study procedure (MONARCH™ mini-PCNL), and none of these components may be used to perform or assist in any other procedure outside of the context of this study (e.g., survey of the contralateral kidney, ureteroscopy in the contralateral kidney).**

[figure not shown]
The site Principal Investigator will determine eligibility and will explain the study to qualified subjects prior to obtaining consent. The subject will also be given an opportunity to review and sign documentation of privacy compliance and authorization according to established practice of the institutions. All subjects are required to meet the inclusion/exclusion criteria defined in the Sections 4.1 and 4.2 in order to be considered eligible for participation in this study. The study flowchart is shown in Figure 1.

The electronic version of this document is stored in Agile PLM and is considered the controlled copy.

Printed copies are for reference only and considered UNCONTROLLED.

CONFIDENTIAL AND PROPRIETARY OF AURIS HEALTH, INC.

	PROTOCOL		Doc #:	104-016667-00
	Monarch Uro - Post-Operative Outcomes Study (2023-URO-0001)		Rev:	C
			Page:	16 of 52

**Figure 1.** Schematic of Study Design

	PROTOCOL	Doc #:	104-016667-00
	Monarch Uro - Post-Operative Outcomes Study (2023-URO-0001)	Rev:	C
		Page:	17 of 52

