## 1.2 Synopsis of Trial

### Post-Operative Outcomes following the Treatment of Kidney Stones with the MONARCH™ Platform, Urology

Primary Objective	The aim of the study is to assess the successful completion of robotic mini-Percutaneous Nephrolithotomy (PCNL) using the MONARCH™ Platform, Urology. This study will also assess stone clearance (Post-Operative Day 30) and the safety profile following this procedure.
Additional Objectives	Additional objectives include exploring immediate post-operative outcomes (Day 1) and patient-reported outcomes. Data gathered from this study will also be used to optimize the robotic platform.
Test Device	The MONARCH™ Platform, Urology and its accessories are intended to access and visualize anatomical locations within the urinary tract and interior of the kidney of adolescents and adults, age 12 and up, for diagnostic and therapeutic procedures with transurethral or transurethral access in conjunction with percutaneous access routes.
Control Device	None
Indication for Use:	The MONARCH™ Platform, Urology, the ureterscope, and endourology accessories are indicated to provide endoscopic visualization and access of organs, cavities, and canals in the urinary tract (urethra, bladder, ureter, calyces, and renal papillae) with transurethral access or transurethral access in conjunction with percutaneous access routes. It can also be used in conjunction with endoscopic accessories to perform various diagnostic and therapeutic procedures in the urinary tract.
Hypotheses	No formal statistical hypotheses are defined.
Study Design	A prospective, single arm observational multicenter study to collect outcomes data on the robotic-assisted mini-PCNL removal of kidney stones using the MONARCH™ Platform – Urology system.
Number of Subjects	The study will enroll up to 60 subjects.
Site	Up to 3 sites
Duration of Study	The total duration of the study is expected to be up to 21 months. The enrollment is expected to take up to 18 months and includes a post-procedure follow-up at 1-day, 30-days, and 90 days for each enrolled participant.

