### 8.2 Levels of Significance

No hypotheses are specified for this study and no p-values are being calculated, therefore no level of significance is specified. All estimation of endpoints will be performed using 95% confidence intervals.

The electronic version of this document is stored in Agile PLM and is considered the controlled copy.

Printed copies are for reference only and considered UNCONTROLLED.

CONFIDENTIAL AND PROPRIETARY OF AURIS HEALTH, INC.

	PROTOCOL	Doc #:	104-016667-00
	Monarch Uro - Post-Operative Outcomes Study (2023-URO-0001)	Rev:	C
		Page:	30 of 52

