### 8.5 Analyses to be Conducted

Categorical variables will be summarized descriptively by frequencies and associated percentages. Continuous variables will be summarized descriptively by number, mean, standard deviation, median, minimum, and maximum. Confidence intervals will also be provided for procedure-related variables. Demographic data will be summarized at the subject level, whereas procedure-related data (including patient-reported outcomes) will be summarized at the procedure level. Any deviations from this general approach will be detailed in the SAP.

Subject disposition will be summarized in total using counts and percentages. The number and percentage of subjects completed and discontinued will be tabulated along with the specific reasons for discontinuation. Subject demographics and surgical characteristics will be summarized.

The number and percentage of procedures achieving successful completion of the robotic-assisted kidney stone removal procedure will be summarized and an exact 95% confidence interval will be estimated.

The number and percentage of procedures resulting in a subject who is determined to be stone free at Day 30 will be summarized and a 95% confidence interval will be estimated. Similar analyses will be performed for the stone-free rate at Day 1. Patient reported outcomes will be analyzed with methodology consistent to the recommendations of the published outcome measure.

All device-related and procedure-related AEs reported during the study will be coded to the Medical Dictionary for Regulatory Activities (MedDRA). All AEs will be summarized by MedDRA system organ class and preferred term by procedure group and in total. Separate summaries will be provided for device-related and procedure-related AEs. Serious AEs will be summarized in a similar manner. Separate summaries by system organ class and preferred term may be provided for events classified as major (Clavien-Dindo Class III or higher) and minor (Clavien-Dindo Class I or II). Separate summaries by Clavien-Dindo grade will be summarized.

Summary statistics will be provided for additional exploratory data points collected in this study. All summaries will be performed only on subjects undergoing the scheduled procedure and only observed data will be summarized. There will be no imputation of data for early terminated subjects or for missing data within the database.

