## 8.5 Primary Endpoint and Associated Hypotheses

No formal hypotheses are specified for this study.

The primary endpoint is the successful completion of the robotic-assisted kidney stone removal procedure, defined as using robotic-assistance provided by the MONARCH™ Platform, Urology to achieve the following procedure milestones:

- Gain safe concomitant (i.e., retrograde and antegrade) access to the upper urinary tract
- Locate and visualize the kidney stones
- Enable fragmentation of stones by standard of care method
- Evacuate stone fragments and dust
- Complete treatment without need for case conversion, as assessed by the investigator

As indicated in the study protocol, the above bulleted device endpoints will be assessed regardless of clinical outcome (e.g., evacuation of stone fragments and dust may still be achieved by the device even if the patient is not stone free). Additionally, these milestones are considered successfully achieved if done so using robotic assistance provided by the MONARCH™ Platform, Urology at any point during the procedure (e.g., location and visualization of kidney stones may still be achieved with robotic assistance, even if the Investigator occasionally chooses to drive the ureteroscope manually due to physician preference.) Alternatively, an early termination of the robotic procedure due to malfunction of the robot, and a subsequent conversion of the case to conventional procedure, would indicate that “complete treatment without need for case conversion, as assessed by the physician” had not been achieved.

The number and percentage of subjects experiencing successful completion will be summarized and an exact 95% confidence interval will be estimated. Counts and percentages will also be provided for each of the four components of the primary endpoint.

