## 8.6 Secondary Endpoints and Associated Hypotheses

The following secondary endpoints are specified for this study:

- Stone free rate ( $\leq 4$  mm residual fragments, measured 30-days post-operative)
- Adverse events through 90-days post-operative, scored on the Clavien-Dindo scale
- Conversion to conventional treatment methods due to study device-related safety event

No associated hypotheses are specified.

The stone free rate will be computed as the percentage of patients who are stone free assessed by computed-tomography (CT) scan at post-operative Day 30. Stone free is defined as having  $\leq 4$  mm residual cumulative stone burden detected by CT. Patients who are found to not have any residual stone fragments at Day 1, will not undergo a second CT at post-operative Day 30, and will be presumed to be stone free at Day 30 for this calculation. The number and percentage of procedures resulting in a subject who is determined to be stone free at Day 30 will be

summarized and a 95% confidence interval will be estimated. Similar analyses will be performed for the stone-free rate at Day 1.

All adverse events will be captured up to post-operative Day 90, at which point the subject exits the study. Summaries will be provided for all adverse events by MedDRA System Organ Class and Preferred Term. Similar summaries will be provided for device-related AEs, procedure-related AEs, serious adverse events (SAEs), device-related SAEs, and procedure-related SAEs. Adverse events will also be scored on the Clavien-Dindo scale and summaries will be provided by System Organ Class and Preferred Term for events that are graded at III or higher on the Clavien-Dindo scale and then similarly for those that are Grade II or lower in a separate output table.

The number and percentage of procedures converted to conventional stone removal procedures (e.g., ureteroscopy or percutaneous nephrolithotomy) due to the occurrence of a study device-related safety event will be summarized. A qualifying safety event is a study device-related adverse event that occurs during the study procedure that prompts the physician to abort the study procedure and pursue a conventional stone removal procedure.

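### Second-kidney procedures may be pooled with first procedures, with no rule for two procedures in one subject and no consistent unit of analysis between protocol and SAP

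*Protocol*

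**What the plan says.** Protocol 3.2 allows bilateral treatment within the study: "A subject may obtain the study procedure in both kidneys at the discretion of the Sponsor". The Sponsor must review the case beforehand, and the only stated criterion is that "the timing of the second study procedure is reasonably not expected to interfere with the interpretation of results from the previous procedure". No maximum number of second procedures is set. The enrolment limit counts people ("The study will enroll up to 60 subjects"), so second procedures come on top of it. Protocol 3.2 refers the reader to Section 8.5 for the analysis.

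Protocol 8.5 answers only by choosing a unit: "procedure-related data (including patient-reported outcomes) will be summarized at the procedure level". For the primary endpoint, "The number and percentage of procedures achieving successful completion of the robotic-assisted kidney stone removal procedure will be summarized", with an exact 95% interval. The stone-free rate is also counted per procedure with a 95% interval. Protocol 8.2 adds: "All estimation of endpoints will be performed using 95% confidence intervals".

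SAP 8.5 changes the primary unit: "The number and percentage of subjects experiencing successful completion will be summarized and an exact 95% confidence interval will be estimated". SAP 8.6 keeps procedures for the stone-free rate: "The number and percentage of procedures resulting in a subject who is determined to be stone free at Day 30". It treats the Day 1 rate in the same way, without naming the interval method, and it counts conversions per procedure. SAP 8.15 counts procedures in the exploratory stone-free cohorts. SAP 6 defines the analysis set by subjects, and SAP 8.4 tabulates left or right kidney per subject with no category for both. SAP 8.12 plans no sensitivity analysis.

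**The concern.** Two procedures in one patient share anatomy, stone type, surgeon and site, so their outcomes may well be correlated. A binomial interval on pooled procedures assumes that they are not, and so claims more information than the patients supply.

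There is also a selection question. The timing condition implies that the procedures are sequential. The study is single-arm and unblinded, completion is assessed at the procedure itself, and the party that approves the second case also analyses the data (Protocol 8). Nothing in the plan shields approval from the first outcome. If patients whose first procedure went well are more likely to have a second, they are counted twice, and a pooled rate drifts upward when outcomes correlate.

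The primary endpoint has a separate gap. Protocol and SAP use different units, and the SAP does not say how to classify a subject with one completed and one failed procedure. None of this concerns whether a second kidney should be treated, which is a clinical matter.

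**Working it through.** Neither document gives a power, precision or expected-rate figure, so there is none to reproduce. The first-procedure success probability p, the within-subject correlation ρ and the frequency of second procedures below are all assumptions.

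**1. Bias if a second kidney follows only a first success.** Let f be the share of first successes that go on to a second procedure. Second-procedure success is s = p + ρ(1−p), and the pooled rate is (p + f·p·s)/(1 + f·p).
- Low end, p = 0.85, ρ = 0.3, f = 0.1: s = 0.895; (0.85 + 0.085 × 0.895)/1.085 = 0.8535, or +0.35 points.
- High end, p = 0.70, ρ = 0.5, f = 0.5: s = 0.85; (0.70 + 0.35 × 0.85)/1.35 = 0.7389, or +3.9 points.
- With ρ = 0, s = p and the bias is zero.

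**2. Loss of information without selection.** With 60 subjects, b of them bilateral, the design effect is DE = 1 + 2bρ/(60+b), and the standard error is understated by √DE.

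| b | ρ | DE | √DE | effective n / procedures |
|---|---|---|---|---|
| 6 | 0.2 | 1.036 | 1.018 | 63.7 / 66 |
| 6 | 0.5 | 1.091 | 1.044 | 60.5 / 66 |
| 12 | 0.5 | 1.167 | 1.080 | 61.7 / 72 |
| 12 | 0.8 | 1.267 | 1.125 | 56.8 / 72 |
| 30 | 0.5 | 1.333 | 1.155 | 67.5 / 90 |

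**3. What the interval looks like.** One procedure per subject: 48/60 = 80.0%, Clopper-Pearson 67.7% to 89.2%, width 21.5 points. Pooled with 12 second kidneys: 58/72 = 80.6%, 69.5% to 88.9%, width 19.4 points. The width ratio is 19.4/21.5 = 0.90, so the interval is about 10% narrower. At ρ = 0.5 the 72 procedures carry the information of about 62.

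**4. Coverage of the naive exact 95% interval.** Simulation with 60 subjects, p = 0.8 and 20,000 runs per scenario. Under selection, the share is of first successes.

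| Share with a second kidney | ρ | no selection | only after a success |
|---|---|---|---|
| 10% | 0.5 | 96.1% | 96.4% |
| 20% | 0.5 | 95.1% | 95.6% |
| 20% | 0.8 | 94.2% | 94.7% |
| 50% | 0.5 | 92.9% | 92.1% |
| 50% | 0.8 | 90.8% | 84.6% |

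With 40 subjects, p from 0.70 to 0.85, ρ from 0.3 to 0.5 and selection, coverage is about 95 to 97% when 10 to 24% of successes go on. The minimum is about 92% when half do.

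**5. Which outputs are affected.**

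| Rate | Protocol 8.5 | SAP |
|---|---|---|
| Completion | procedures, exact interval | subjects, exact interval (8.5) |
| Stone free, Day 30 and Day 1 | procedures, interval | procedures, interval, method not named (8.6) |
| Conversion | not listed separately; general procedure-level rule | procedures, no interval (8.6) |
| Stone-free cohorts | not listed | procedures, no interval (8.15) |

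**The case against.** A reader might infer that the Sponsor approves second kidneys knowing the first result, so that the reported rates are inflated and their intervals too narrow. The documents do not support that. Protocol 3.2 does not say that approval follows sight of the first outcome, and a bilateral plan could be reviewed before either procedure. Upward bias needs both outcome-dependent approval and positive correlation, and neither is established.

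Other limits also stand. The SAP already reports the primary endpoint by subject, so the pooling criticism of that endpoint applies to the protocol text only. Conversion and the SAP 8.15 cohorts have no interval in the SAP. Adverse-event summaries are not stated to use a procedure denominator, so it cannot be said that complication rates are diluted.

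Bilateral cases may be few. Exclusion criterion 2 bars expected additional procedures that might affect the results, and SAP 8.4, written after enrolment had stopped, has no bilateral category. The exact interval's conservatism absorbs small numbers. A more striking example is easy to build: 34/40 becoming 42/48 narrows the interval by 15%. But that needs all eight second kidneys to succeed, whereas the step 1 formula at p = 0.85 expects 8 × 0.895 = 7.2 to 8 × 0.925 = 7.4.

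Finally, the study is descriptive, with no hypothesis or threshold. This limits the consequence. It does not remove the gap: Protocol 3.2 foresaw two procedures per subject and deferred the handling to a section that gives no rule beyond the unit of counting.

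**Conclusion.** The point holds as a gap in the analysis rules and an uncontrolled risk, not as a demonstrated bias. The text establishes that second procedures are discretionary and uncapped, that stone-free and conversion rates are counted per procedure with no within-subject rule, that the primary endpoint's unit differs between protocol and SAP, and that no planned output would reveal an effect.

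The size depends on inputs that the documents do not give. Under p of 0.70 to 0.85, ρ of 0.3 to 0.5, and 10 to 50% of first successes going on to a second kidney, the upward bias is about 0.4 to 3.9 points, and zero if ρ is 0. In the scenarios examined, coverage of an exact interval falls noticeably below 95% only when about half of subjects are bilateral. With few bilateral cases the numerical effect is small. The change is still worth making, because it is cheap and also settles the unit of analysis.

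**What to change.** In SAP 8.5, 8.6 and 8.15, base the completion, stone-free and conversion rates on each subject's first study procedure. Use an exact (Clopper-Pearson) 95% interval wherever an interval is planned, and name that method for the Day 30 and Day 1 stone-free rates. State that this departs from the procedure-level rule in Protocol 8.5. Report the number of bilateral subjects, add a both-kidneys category to the side table in SAP 8.4, and tabulate second-kidney procedures separately. An all-procedures rate may be added as supportive, but only with an interval that accounts for clustering by subject.

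The cost is a first-procedure flag and a few sentences in the SAP. Any second procedures leave the main denominator, so the interval is slightly wider than the pooled one. First-procedure reporting also removes the question of how to classify a subject with one success and one failure.
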